7.8.2. Outcome Endpoints

7.8.2.1. Neuropsychological evaluations

Neuropsychological testing will be performed at baseline and yearly as described in Section 7.7.1. Data will be quantitative. The primary outcome variable is the score on the Hopkins Verbal Learning Test.

7.8.2.2. MRI of Brain

MRI will be performed at baseline and yearly as described in Section 7.7.2. Volumetric data and scoring for white matter changes and perivascular spaces will be quantitative. Diffusion tensor imaging and tractography data will be quantitative. Analysis of MRI results will be performed at the end of the study; however, if there are incidental findings of clinical significance found during the study, these will be reported to the PI.

7.8.2.3. Clinical Evaluations

7.8.2.3.1. History and Physical Examination

A detailed and thorough medical history will be obtained at screening as described in the methods. Data will be qualitative.

A detailed and thorough physical examination will be performed at each visit as described in the methods. Data will be qualitative.

Any clinically significant worsening from the baseline medical status and vital signs status will be documented as an AE on the appropriate data collection sheet and will be followed as an adverse event consistent with the procedure outlined in Section 11.3. Clinical significance is defined as any variation in physical findings that has medical relevance and results in an alteration in medical care.

7.8.2.3.2. Neurologic examinations

A full neurologic examination including mental status, cranial nerves, motor, sensory, associated motor, and reflexes will be conducted at each visit throughout the study period (refer to Section 7.7.3.2 for further information). Data will be qualitative.

7.8.2.3.3. Six minute walk test

The six minute walk test will be performed at each visit. Borg scale results for before and after the test will be kept as ordinal variables for each subject at each

visit. Before and after results will be compared at each visit to determine change over time.

The distance walked and laps walked will be continuous variables. Means and standard deviations for the changes made by the subjects over the study period will be calculated.

7.8.2.3.4. Subjective improvement

Subjective accounts will be recorded and kept as qualitative data.

7.8.2.3.5. Independence of functioning scale

Functional Independence Measure (FIM) score will be performed at each visit (Maynard et al., 1997). The FIM score is calculated as described in Appendix B. Change in the FIM score for each subject with time will be calculated.

7.8.2.4. Laboratory tests

CSF GAG content

At the each lumbar puncture, a portion of CSF will be quick frozen for subsequent glycosaminoglycan analysis. Sulfated glycosaminoglycans will be assayed using a modification of the Alcian Blue method of Bjornsson as published (Whitley et al., 1989). The GAG quantities will be determined by comparison to standards of dermatan sulfate.

7.8.2.4.1. CSF ELISA for α -L-iduronidase specific antibodies

CSF antibody levels will be performed according to the schedule above. Titers will be recorded as OD units/mL. An antibody titer > 20 OD units/mL is considered positive. Data will be kept as quantitative, continuous variables, and each subject assessed for change over the study period. A mean and standard deviation for the pre and post-treatment antibody levels may be calculated. Titers will be sent for analysis every six months.

7.8.2.4.2. Serum ELISA for α -L-iduronidase specific antibodies

Serum antibody levels will be performed according to the schedule above. Titers will be recorded as OD units/mL. An antibody titer > 20 OD units/mL is considered positive. Data will be kept as quantitative, continuous variables, and each subject assessed for change over the study period. A mean and standard deviation for the pre and post-treatment antibody levels may be calculated. Titers will be sent for analysis every six months.

8. Data and Specimen Banking

CSF and serum specimens will be stored at -20 degrees C without identifiers at Los Angeles Biomedical Research Institute for at least 11 years. Specimens will be accessed for study tests by qualified laboratory personnel. Access to specimens by other investigators will be granted contingent upon IRB approval and informed consent of study participants.

The clinical information collected for this study will be stored at the Data Management and Coordinating Center at the University of South Florida in Tampa, FL and also sent to a Federal data repository. All retrospective data (from the beginning of the study) and all ongoing prospective data will be collected. The data management center uses several layers of protection for the clinical data stored there. It meets all of the local and federal security requirements for research datacenters. Information is stored only using a study ID.

While the study is active, access to the stored data and specimens will be limited to approved study staff. After the study is closed, local access will be limited to the site's Principal Investigator(s). Authorized study staff with access to stored specimens and/or data have completed training that included GCP, HIPAA, and if applicable, an overview of the study database. Access to the data by other investigators will be granted contingent upon IRB approval and informed consent of study participants

Data to be stored for each study participant include:

- Medical history and physical
- Neurologic examination including mental status, cranial nerves, motor, sensory, associated motor, and reflexes
- Standard blood CBC and comprehensive metabolic panel chemistries
- Blood serum chemistries, including electrolytes (sodium, potassium, chloride, calcium), bicarbonate, glucose, BUN, creatinine, magnesium, phosphate, hepatic enzymes (AST and ALT), total protein, albumin, bilirubin, and alkaline phosphatase. Other chemistries may be obtained if clinically indicated in the opinion of the investigator.
- Coagulation studies, including prothrombin time (PT), partial thromboplastin time (PTT), and international normalized ratio (INR)
- CSF glucose, protein, and cell counts
- CSF opening pressure
- ELISA anti-IDU antibody
- Serum glycosaminoglycans (GAG) levels

- Brain MRI data, including white matter changes and Virchow-Robin spaces, volumes, diffusion tensor imaging and tractography
- Hopkins Verbal Learning Test
- Six minute walk test with Borg scale results
- Functional Independence Measure (FIM) score
- Subjects' subjective improvement scores
- Global assessment score based on subject's clinical assessments, laboratory studies, neurophysiologic assessments, and imaging studies

9. Data Management

9.1. Overview

This study will evaluate changes in neuropsychological, radiological, clinical, biochemical measures, and safety after 5 years of intrathecal injections of rhIDU in six MPS-I subjects. The statistical goal is estimation of the magnitude of these changes and their heterogeneity and calculation of rates of adverse events.

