The study will be conducted at the Los Angeles Biomedical Research Institute at Harbor-UCLA (LAB-HUCLA), Children's Hospital Oakland Research Institute

(CHORI) and the University of Minnesota (UMN). Additional study sites may be added as subjects are identified. Specific details are below:

- Recruitment: Subjects will be recruited from participants in the MIRC-002 study at LAB-HUCLA and CHORI.
- Procedures: Procedures will be performed at LAB-HUCLA, CHORI, and additional study sites that are added as subjects are recruited to the study. The addition of any new study site will be contingent upon approval by their local institutional review board (IRB), and the IRB at LAB-HUCLA. Neuropsychological testing will be performed at UMN.
- Regulations: The IRBs at CHORI and UMN will oversee the research at these respective sites, with LAB-HUCLA the primary site responsible.

4. Resources Available to Conduct the Human Research

Since subjects will be recruited from among participants enrolled in the pilot (MIRC-002) study:

- All participants are accessible for recruitment
- 67% are anticipated to be enrolled in the proposed study
- Study staff have previously been involved with participants and their families through the pilot study, so are familiar with local culture and attitudes toward clinical research.

Time requirement for the Principal Investigator to conduct and complete the proposed study within the agreed trial period is projected to be 8 hours per week.

Site study staff at the LAB-HUCLA include six members: two co-Primary Investigators, two pharmacists, one Study Coordinator, and one laboratory staff. Study staff at the CHORI site include three members: one site PI, one pharmacist and one study coordinator. Study staff at the UMN include two members: one site PI and one study coordinator. All study staff have completed appropriate training regarding protection of human research subjects, Good Clinical Practices, and HIPAA, and have previously participated in other clinical research trials.

Inpatient study treatments are conducted at the hospital in an area designated for clinical research and study evaluations are completed in separate outpatient clinical research facilities. Principal Investigators have hospital privileges at their respective sites and non-study staff resources are available at each hospital should study participants require medical or psychological support as a result of an anticipated consequence of the research study.

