6.4. Study Timelines

The duration of each subject's participation in the study is expected to be five years. We anticipate enrolling these subjects over a 4-year period. The estimated date of completion of the study is 10 years following the onset of the study.

7. Procedures Involved in the Human Research

This study is a five-year open-label, prospective trial in 6 MPS I subjects age six years or greater who have completed a 24-month open label study (MIRC-002). Potentially eligible subjects who (or, if appropriate whose parents or guardians) have provided signed, written informed consent will first participate in a baseline screening phase. This will occur at least six months after subjects have completed the MIRC002 pilot study. During baseline screening, the subjects will receive the baseline evaluations outlined below, and their eligibility will be determined. Every three months, subjects will receive intrathecal recombinant human α-L-iduronidase (IT rhIDU) approved as Aldurazyme® [laronidase] for the treatment of cognitive impairment in patients with mucopolysaccharidosis I (MPS I). Neuropsychological testing and MRI will be performed at baseline and at one year intervals. Safety will be monitored continuously throughout the subject's study participation through recording all adverse events (AEs) and periodically performing clinical and laboratory evaluations.

Study subjects will receive intrathecal enzyme therapy only during the study; intrathecal enzyme therapy will not be administered at the end of the five-year period. If further intrathecal enzyme is desired, the subject may enroll in further intrathecal research if another study is available.

To assure that subjects enrolling in the trial have maximum access to alternative therapy, subjects will be asked to receive counseling regarding other available appropriate medical and surgical alternatives prior to enrollment in this trial.

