7.2. Schedule of Study Evaluations

After obtaining informed consent, the investigator will conduct the study as outlined in the following sections. Table 1 summarizes the nature of the assessments and treatments and their timelines. Refer to Study Operations Manual for guidelines regarding test assessments and procedures for handling/shipment of all central laboratory samples.

Table 1 Schedule of study assessments and treatments

Month Number	Baseline	Visit 1/Odd Numbered Visits	Visit 2/Even Numbered Visits	End Study
Neuropsychological testing	X		yearly	
MRI of brain	X		yearly	
Clinical tests				
History and Physical examination	X	X	X	X
Neurologic examination	X	X	X	X
Photography and video (optional)	X	X	X	X
Six-minute walk test	X	X	X	X
Subjective response of clinical symptoms	X	X	X	X
FIM scoring	X	X	X	X

Laboratory tests (CSF)				
Protein, glucose, cell count		X	X	
GAG levels		X	X	
Anti-rhIDU antibody		X	X	
CSF iduronidase assay		X	X	
Laboratory tests (blood)				
Anti-rhIDU antibody	X	X	X	X
CBC, Chem panel 20, Coagulation studies	X	X	X	X
Neurophysiologic test				
CSF flow study	X			
Investigator Global Assessment				
	X	X	X	X
Treatments				
Intrathecal rhIDU		X	X	

Visits occur at three-month intervals starting from Visit One. There may be a variable period between Baseline/Screening and Visit One from five days to three months. If the period between Baseline/Screening and Visit One is less than one week, then all of the other assessments do not need to be repeated for Visit One.

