9.2. Study Size

A study size analysis was done for the pilot study. As this study is only open to subjects that have completed the pilot study, the maximum number of subjects available for this study is six.

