9.3.3.2. History and physical examination

At each visit, each subject will be classified as experiencing an adverse event if clinically significant worsening from baseline medical status, as described in Section 7.8.1.1, has occurred. The frequency and percent of subjects experiencing such an event will be tabulated for each visit.

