9.3.3.4. Other Adverse Events

Other adverse events and unexpected adverse events from the time of injection to the time of subsequent injection will be recorded for each subject. The frequency and percent of subjects experiencing any such event will be tabulated for each post-injection interval, and for the entire month 0 to end study interval.

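### Adverse event rates are a stated goal, but Section 9.3.3 plans only percentages of at most six subjects, with no event count, exposure denominator, pooling or interval

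*Combined protocol and SAP*

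**What the plan says.** Section 9.1 gives the statistical goal as estimating the size and heterogeneity of changes, together with "calculation of rates of adverse events". It states no unit or denominator for a rate.

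The adverse event summaries are in Section 9.3.3:

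- **9.3.3.2 (history and examination findings).** The classification rule begins "At each visit, each subject will be classified as experiencing an adverse event if clinically significant worsening from baseline medical status". The planned summary of that classification reads "The frequency and percent of subjects experiencing such an event will be tabulated for each visit".
- **9.3.3.3 (blood count and chemistry).** The same structure: each visit is judged against baseline, with the number and percent of subjects per visit.
- **9.3.3.4 (other adverse events).** "The frequency and percent of subjects experiencing any such event will be tabulated for each post-injection interval", and once more for the whole study.

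None of these gives a count of events, a total exposure, a rule for counting an event once, or a confidence interval. By contrast, 9.3.3.1 plans 95% confidence intervals for the CSF and antibody changes.

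The ingredients for a rate are collected. Section 9.3.2 summarises time enrolled and number of intrathecal doses, but under study conduct and not as a denominator. Section 12.3 has onset and resolution dates and times entered on the CRF for every event.

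**The concern.** Long-term safety is the first objective in Section 1. A reader of the results will want to know how often an injection is followed by an event, how many events occur per year of treatment, and how precisely each is known. As planned, the reader gets percentages of at most six people.

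- The whole-study percent gives a subject with one event the same weight as a subject with twenty. It also gives a subject who leaves early the same weight as one who completes five years.
- The per-interval percents respond to the rate, but they form about 20 separate tables of at most six subjects, each moving in steps of 100/6 = 16.7 points. They are not pooled.
- The by-visit percents in 9.3.3.2 and 9.3.3.3 describe who is worse than baseline at that visit. If they are read as new events, one lasting change appears again at every later visit.

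**Working it through.** The plan states no adverse event rate, precision or sample size for safety, so there is no figure of its own to reproduce. Event rates below are assumptions, shown over a range.

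**Inputs from the documents**

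- Subjects: "the maximum number of subjects available for this study is six" (9.2). Section 4 says "67% are anticipated to be enrolled in the proposed study"; 67% of 6 is about 4, used as the lower scenario.
- Follow-up: "The duration of each subject's participation in the study is expected to be five years" (6.4).
- Injection interval: "Visits occur at three-month intervals starting from Visit One" (7.2), so 5 × 4 = 20 injections per subject (21 if both ends are counted).
- Exposure if all complete: 6 × 20 = 120 injections and 6 × 5 = 30 patient-years, or 4 × 20 = 80 and 4 × 5 = 20.

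**1. Saturation of the whole-study percent.** At a constant rate r per patient-year, the chance of at least one event is 1 − exp(−5r) over five years and 1 − exp(−r/4) over one three-month interval.

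| Assumed r | Five years | One interval |
|---|---|---|
| 0.05 | 22% | 1.2% |
| 0.1 | 39% | 2.5% |
| 0.5 | 92% | 12% |
| 1 | 99% | 22% |
| 2 | about 100% | 39% |

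From 0.5 to 2 per year the five-year percent hardly moves, while the interval percent does. At the low rates the five-year percent does not saturate. Moderate rates are plausible for any event, since Section 12.1 defines adverse events broadly and 12.7 tracks routine illnesses and headaches as adverse events. They are not implied for rare or serious types.

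**2. What the whole-study cell hides.** Suppose all six complete and all are affected, so the entry is 6/6 (exact 95% lower limit 0.025^(1/6) = 54%). Illustrative counts over 30 patient-years, with exact Poisson 95% intervals:

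- 6 events: 6/30 = 0.20 per year (0.07 to 0.44)
- 60 events: 60/30 = 2.0 (1.53 to 2.57)
- 120 events: 120/30 = 4.0 (3.32 to 4.78)

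With four completers and an entry of 4/4, 4 events give 4/20 = 0.20 (0.05 to 0.51) and 40 give 40/20 = 2.0 (1.43 to 2.72).

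**3. Unequal follow-up.** At r = 1, a subject followed for one interval has a 22% chance of being counted, and a completer 99%. The whole-study percent treats them alike.

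**4. Prevalence in the by-visit tables.** On the natural reading of 9.3.3.2 and 9.3.3.3, a worsening that starts at visit k and never resolves is shown at 21 − k of 20 visits. Starting at visit 4, that is 17 visits for one event.

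**5. Event type never observed.** The two-sided 95% upper limit is 1 − 0.025^(1/n) for a proportion and −ln(0.025)/T = 3.69/T for a rate.

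| | 6 completers | 4 completers |
|---|---|---|
| Percent of subjects | 46% (0/6) | 60% (0/4) |
| Per injection | 3.0% (0/120) | 4.5% (0/80) |
| Per patient-year | 0.12 (0/30) | 0.18 (0/20) |

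The last two rows assume independence between injections, or over time, within a subject.

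**The case against.** The strongest reply is that 9.3.3.4 already comes close to a per-injection measure. Each subject receives one injection per interval, so the number affected in an interval is the number of injections followed by at least one event, and adding the intervals gives a pooled proportion. A reader might infer from 9.3.3 that the tables cannot show how often an injection is followed by an event; the documents do not support that. What remains missing is the pooling itself, an interval estimate, any count of several events within one interval, and a rate over time. The table also covers only the other adverse events, not those classified under 9.3.3.2 and 9.3.3.3.

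A reader might also infer that the whole-study percent approaches 100% whatever the true rate. It does not: 22% is expected at 0.05 per year. Saturation concerns that one summary and depends on an assumed rate.

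It may also be said that rate is often used loosely for percent affected, so that 9.3.3 simply gives the content of the phrase in 9.1. That is fair. The term is undefined, and the two sections do not flatly contradict each other.

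On recounting, no sum over visits is planned, so nothing in the plan inflates a total. Section 7.8.1.1 requires that worsening lead to a change in care, so a stable, already managed change might not be reclassified at each visit. The point matters only if the by-visit tables are read as incidence.

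Finally, with at most six subjects, event-level reporting of the kind in Section 12.7 will carry much of the safety information. That is true, but a listing does not supply a rate or its uncertainty.

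**Conclusion.** The point holds in limited form. Section 9.1 sets adverse event rates as a goal, and 9.3.3 defines no rate: it plans subject percentages without event counts, exposure, pooling or intervals, although the data for all of these are collected. This is worth correcting in the analysis plan. It does not affect the conduct of the trial.

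The cost of leaving it is clearest for event types that are not seen. The subject-level statement excludes only frequencies above 46% (six completers) or 60% (four), whereas the exposure-based limits are 3.0% to 4.5% per injection and 0.12 to 0.18 per patient-year. Those figures rest on every enrolled subject completing five years with about 20 injections, and on independence within subject. Early withdrawal or clustering would widen them. Saturation of the whole-study any-event percent is likely at moderate rates but rests on assumed rates, and it does not extend to rare or serious types or to the per-interval tables.

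**What to change.** Keep the planned subject percentages and make these changes to 9.3.3:

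- Define the rate meant in 9.1.
- Count each event once, by date of onset, and report the number of events and of subjects affected, overall and by type and seriousness.
- Divide the event counts by total injections and by total patient-years, using the exposure data already summarised under 9.3.2.
- Give 95% intervals that allow for clustering within subject, or give exact intervals labelled as assuming independence.
- Label the tables in 9.3.3.2 and 9.3.3.3 as prevalence of worsening from baseline by visit.

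The cost is a few extra table rows and no new data collection. The drawback is that the intervals will be too narrow if events concentrate in a few subjects and this is not allowed for. With four to six subjects any clustered interval will itself be rough, so the number of events per subject should be shown beside it.

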9.2. Study Size

A study size analysis was done for the pilot study. As this study is only open to subjects that have completed the pilot study, the maximum number of subjects available for this study is six.

9.3. Data analysis methods

A descriptive summary of subject characteristics at baseline will be made with frequencies and percentages for categorical variables, and with mean and standard deviation or median and quartiles, depending on statistical distribution, and range for continuous measurements. Some analyses specified below require that continuous observed or derived measures have statistical properties such as normal distributions. If there is evidence that statistical requirements are not met, transformations to achieve those requirements will be performed. If such transformations are not possible, non-parametric analogues to the proposed parametric methods will be substituted.

